11.6. Appendix 6: Derived and Transformed Data

11.6.1. General

Multiple Measurements at One Time Point

- The last valid value prior to randomization will be used as the baseline value (except diary card)
- The first valid measurement will be used for post-randomization visits in any derivation of summary statistics but if listed, all data will be presented.

Study Day

When calculating the number of days relative to the date of randomization (i.e., treatment start date), the date of randomization will be counted as Day 1. Study day will be calculated as follows:

- Date of the event = Missing → Study Day = Missing
- Date of the event < Start of treatment date → Study Day = Date of the event – Start of treatment date
- Date of the event ≥ Start of treatment date → Study Day = Date of the event – (Start of treatment date) + 1

Date of Completion/Withdrawal

The date of completion/withdrawal will be derived as follows:

- For subjects who complete the last on-treatment study visit, the date of completion/withdrawal will be the date of that visit (Visit 5).
- For subjects who withdraw from the study, the date of completion/withdrawal will be the latest of the date of the last attended scheduled clinic visit (excluding follow-up), the date of the EW visit (if present) and the last dose date.

11.6.2. Study Population

Demographics

Age

- GSK standard IDSL algorithms will be used for calculating age where birth date will be imputed as follows:
 - Any subject with a missing day will have this imputed as day '15'.
 - Any subject with a missing date and month will have this imputed as '30th June'.
 - Age will be calculated based on the screening date.
- Birth date will be presented in listings as 'DDMMMYYYY'.

Body Mass Index (BMI)

- Calculated as $\text{Weight (kg)} / [\text{Height (m)}^2]$

Treatment Compliance Based on Subject Diary Card

The number of doses of study drug taken during the double-blind treatment period will be estimated based on information recorded by the subject on the diary card. Subjects will document their study

Treatment Compliance Based on Subject Diary Card

medication administration/compliance on the diary card by answering the question “Did you spray 2 sprays of your medication in each nostril?” Each occurrence of “yes” in response to this question will count as one dose of study medication. Percent treatment compliance will be calculated for each subject as follows:

$$\% \text{ Treatment Compliance} = \frac{\text{\# of doses used}}{\text{expected \# of doses used}} \times 100\%, \text{ where}$$

- # of doses used = sum of the “yes” responses to the question “Did you spray 2 sprays of your medication in each nostril?” for all days on treatment
- expected # of doses used = # of days on treatment.

Overall compliance will be categorised as follows:

- < 80%
- ≥ 80% to ≤120%
- >120%.

11.6.3. Safety

Extent of Exposure

- Number of days of exposure to study drug will be calculated based on the formula:
Duration of Exposure in Days = (Treatment Stop Date – Treatment Start Date) + 1
- If a subject’s **treatment** stop date is missing it will be assumed to be date of the study discontinuation/completion. If the study discontinuation/completion date is also missing then the extent of exposure will be set to missing.
- If a subject’s **treatment** start date is missing then it will be assumed to be their Day 1 visit date.

Laboratory Parameters

- The baseline value for a parameter will be the most recent recorded value for that parameter before dosing on Day 1.
- Laboratory data values will be classified as ‘low’, ‘normal’ or ‘high’ with reference to normal ranges.
- Laboratory data (haematology, chemistry, and urinalysis) will be collected during Visit 1 (Screening) and Visit 5 (Week 4) / Early Withdrawal. The laboratory data will be summarized by visit. The number and percentage of subjects with laboratory values outside the normal range will be summarized by study visit for each laboratory analyte.
- Shift tables will summarize post-treatment flag values [low (L), normal (N), or high (H)] for each analyte, relative to their baseline flag values. Laboratory values are flagged as “low” if they are less than the lower limit of the normal range, “normal” if they are within the normal range and “high” if they are above the upper limit of the normal range. Baseline is defined as the last laboratory values captured prior to randomization [i.e., at Visit 1 or, where applicable, a repeat assessment performed prior to administration of the first dose of study medication at Visit 2

Laboratory Parameters

(Randomization, Day 1)]. The endpoint is defined as the first post-treatment value (i.e. laboratory value collected at Visit 5 (Week 4) or withdrawal visit). Shift from baseline to endpoint (Week 4 / discontinuation) in laboratory value is categorized, for each laboratory analyte, as follows:

To High	L to H, N to H
To Normal or No Change	L to N, H to N, L to L, N to N, H to H
To Low	N to L, H to L.

The number of subjects in each category will be summarized for each laboratory analyte.

- All laboratory values for subjects with at least one post-treatment laboratory value (Including repeat assessments) outside the normal range will be listed.

Nasal Examinations

- The baseline value for a nasal examination endpoint will be the most recent recorded value for that endpoint before dosing on Day 1.
- Nasal examinations will be collected during Visits 1-5 or Early Withdrawal. Summary statistics for mucosa, septum, secretions, nasal patency, size of any polyps and ulcers will be provided at Visit 1-5 or Early Withdrawal.
- A summary of change from baseline in nasal examinations at endpoint (Vsit5/Early Withdrawal) will be made.

Vital Signs

- The baseline value for a vital sign endpoint will be the most recent recorded value for that endpoint before dosing on Day 1.
- Vital signs will be collected during Visit 1 (Screening) and Visit 5 (Week 4)/Early Withdrawal. Summary statistics for systolic blood pressure (mmHg), diastolic blood pressure (mmHg), heart rate (beats/min), temperature (°C), and respiratory rate (breaths/min) will be provided at baseline and Visit 5 or Early Withdrawal.
- A summary of change from baseline in vital signs at endpoint (Vsit5/Early Withdrawal) will be made.

12-Lead ECG

- The baseline value for an ECG endpoint will be the most recent recorded value for that endpoint before dosing on Day 1.
- Twelve-lead ECGs will be performed at Visit 1 (Screening) and Visit 5 (Week 4)/Early Withdrawal. ECG results of "normal", "abnormal, not clinically significant (NCS)", and "abnormal, clinically significant (CS)" will be summarized at baseline and Visit 5 or Early Withdrawal.
- A listing of subjects with abnormal clinically significant ECG evaluations and/or clinically significant change(s) in ECG evaluations will be provided.

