5.2. Exclusion Criteria

A subject will not be eligible for inclusion in this study if any of the following criteria apply:

[1] Concomitant Medical Conditions

1. Significant concomitant medical conditions, defined as:
 - a. Historical or current evidence of clinically significant uncontrolled disease of any body system. Significant is defined as any disease that, in the opinion of the investigator or which would confound the interpretation of the study results if the disease/condition exacerbated during the study.
 - Significant renal impairment, which based on the opinion of the investigator, would preclude the subjects' participation in the study.
 - Current active liver or biliary disease (with the exception of Gilbert's syndrome or asymptomatic gallstones or otherwise stable chronic liver disease per investigator assessment).

NOTES:

 - Stable chronic liver disease should generally be defined by the absence of ascites, encephalopathy, coagulopathy, hypoalbuminaemia, oesophageal or gastric varices, or persistent jaundice, or cirrhosis.
 - Chronic stable hepatitis B and C (e.g., presence of hepatitis B surface antigen (HBsAg) or positive hepatitis C antibody test result at screening or within 3 months prior to first dose of study treatment) are acceptable if subject otherwise meets entry criteria.
 - b. A severe physical obstruction of the nose(e.g., deviated septum , nasal polyp or frequent bleeding of the nose that could affect the deposition of double blind intranasal study drug
 - c. Current or history of a Candida infection of the nose or oropharynx, shingles, chickenpox, measles, ocular herpes simplex.
 - d. Known hypersensitivity to corticosteroids or any excipients in the product.
 - e. Recent nasal septal surgery or nasal septal perforation
 - f. Subjects start, discontinue or change desensitization treatment within 30 days prior to Visit 1.
 - g. Bacterial or viral infection of the eyes or upper respiratory tract within two weeks of Visit 1 or during the screening period.
 - h. Asthma, with the exception of mild intermittent asthma [[Ruchi, 2009](#)]
 - i. Diagnosis of rhinitis medicamentosa, vasomotor AR or eosinophil rhinitis
2. Abnormal Laboratory Findings: A clinically significant laboratory abnormality

[1] Concomitant Medical Conditions

including Liver Function Tests at Visit 1 meeting the following criteria (as below and further defined in the study procedure manual):

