
ALT \geq5xULN and <8xULN and bilirubin <2xULN without symptoms believed to be related to liver injury or hypersensitivity, and who can be monitored weekly for 2 weeks.
 
OR
 
ALT \geq3xULN and <5xULN and bilirubin <2xULN without symptoms believed to be related to liver injury or hypersensitivity, and who can be monitored weekly for 4 weeks.
	
 • Notify the GSK medical monitor within 24 hours of learning of the abnormality to discuss subject safety. • Subject can continue study treatment • Subject must return weekly for repeat liver chemistries (ALT, AST, alkaline phosphatase, bilirubin) until they resolve, stabilise or return to within baseline • If at any time subject meets the liver chemistry stopping criteria, proceed as described above • If ALT decreases from ALT \geq5xULN and <8xULN to \geq3xULN but <5xULN, continue to monitor liver chemistries weekly. • If, after 4 weeks of monitoring, ALT <3xULN and bilirubin <2xULN, monitor subjects twice monthly until liver chemistries normalize or return to within baseline.

References

12.3. Appendix 3: Definition of and Procedures for Recording, Evaluating, Follow-Up and Reporting of Adverse Events

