
 Unscheduled visits will not be included in summary tables. Unscheduled visits will not be included in figures. All unscheduled visits will be included in listings. 	
Descriptive Summary Statistics	
Continuous Data	Refer to IDSL Statistical Principle 6.06.1
Categorical Data	N, n, frequency, %

Reporting Standards
Graphical Displays

• Refer to IDSL Statistical Principals 7.01 to 7.13.

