11.8. Appendix 8: Values of Potential Clinical Importance

Not applicable

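### The laboratory shift table groups a further rise from an already high value with stable and improved results, and no planned table counts children by arm at the protocol's own ALT and bilirubin multiples

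*SAP*

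**What the plan says.** SAP 11.6.3 (Laboratory Parameters) sets the flags: "Laboratory data values will be classified as ‘low’, ‘normal’ or ‘high’ with reference to normal ranges". There is no grade and no multiple of ULN. The shift from baseline to endpoint then has three rows. To High takes L to H and N to H. To Low takes N to L and H to L. To Normal or No Change takes the other five pairs: "L to N, H to N, L to L, N to N, H to H".

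The post-baseline value is a single one: "The endpoint is defined as the first post-treatment value (i.e. laboratory value collected at Visit 5 (Week 4) or withdrawal visit". SAP 11.6.1 adds that "The first valid measurement will be used for post-randomization visits in any derivation of summary statistics", and SAP 11.5.3 that "Unscheduled visits will not be included in summary tables", although listings keep them. SAP Appendix 8, on values of potential clinical importance, reads "Not applicable".

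Protocol Appendix 2 does use multiples of ULN. An ALT of 8xULN or more is a stopping event. ALT bands from 3xULN and from 5xULN trigger monitoring, or stopping if they persist. ALT of at least 3xULN combined with bilirubin of at least 2xULN (more than 35% direct), with INR above 1.5, or with symptoms is also a stopping event. For children under monitoring, "Subject must return weekly for repeat liver chemistries (ALT, AST, alkaline phosphatase, bilirubin) until they resolve, stabilise or return to within baseline".

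**The concern.** Laboratory results are a named safety endpoint under the secondary objective, which compares both doses with placebo. The shift table is the planned display that is meant to show movement within children, arm by arm. Because its flags stop at high, it cannot tell a small excess from a large one. The row that receives within-high worsening also receives stable values and recoveries from high to normal. A reader who takes the row at its label would count a child who worsened among those who did well.

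The multiples on which the protocol acts are not used as counting thresholds in any planned table. The by-arm incidence that a safety reviewer would look for first has to be rebuilt by hand from listings.

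**Working it through.** The point rests on a classification rule. The plan states no figure to reproduce, so the check applies the rule as printed.

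**Inputs**
- Flags, shift rows and endpoint value: SAP 11.6.3.
- Laboratory schedule: Visit 1, Visit 5 and Early Withdrawal only (Protocol 7.1, Table 2).
- Liver limits: Protocol Appendix 2.
- Entry: Protocol 5.2 accepts "Chronic stable hepatitis B and C" if other criteria are met. Its liver-test exclusion requires ALT above 2xULN **and** bilirubin above 1.5xULN together.
- The ALT paths below are illustrative assumptions, not data.

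**Step 1: coverage of the rule.** Three flags give 3 x 3 = 9 pairs. Two are To High, two are To Low, and 9 - 2 - 2 = 5 are To Normal or No Change. Those five include one worsening that the flags cannot see (rises within H to H), its mirror image (falls within L to L), and one clear improvement (H to N).

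**Step 2: ALT paths through the rule (xULN, no unscheduled values).**

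| Baseline | Visit 5 or withdrawal | Fold rise | SAP row |
|---|---|---|---|
| 1.1 | 8.0 | 8.0/1.1 = 7.3 | To Normal or No Change |
| 1.5 | 8.5 | 8.5/1.5 = 5.7 | To Normal or No Change |
| 2.0 | 8.5 | 8.5/2.0 = 4.3 | To Normal or No Change |
| 2.5 | 8.5 | 8.5/2.5 = 3.4 | To Normal or No Change |
| 0.8 | 8.5 | 8.5/0.8 = 10.6 | To High |
| normal | 1.1 | small | To High |

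The gap needs a baseline above ULN. With bilirubin at 1.0xULN, none of these baselines meets the liver-test exclusion, because both limbs are required.

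**Step 3: what the other displays show.**
- Tables 3.22 and 3.23 (chemistry, absolute and change, by arm): Protocol 9.4 requires the maximum, so a large value or change would appear as an arm extreme. The mean would barely move: a rise from 1.9 to 8xULN in one of 120 children shifts it by (8 - 1.9)/120 = 0.05xULN. Reference ranges are local (Protocol 7.5.6), so a maximum in raw units does not translate directly into a multiple of ULN.
- Tables 3.30 and 3.31 (outside normal range): the child counts as abnormal at both visits, so no movement is visible.
- Listing 12: all values, including repeats, for a child with an abnormal post-treatment value.
- Adverse event tables: the combined ALT/bilirubin and ALT/INR events must be reported as SAEs (Protocol Appendices 2 and 3). An isolated ALT rise enters only if the investigator judges it clinically significant.
- The display list in SAP Appendix 14 has no table by ULN multiple and no liver event table.

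**Step 4: unscheduled values.** Take baseline 0.8 and an unscheduled 8.5xULN. If the Visit 5 or withdrawal value is 0.9, the row is To Normal or No Change; if it is 1.2 or 8.5, the row is To High. This route therefore needs a mid-treatment draw that is not on the schedule, followed by a return to range before the scheduled one.

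**Step 5: which remedy works.** Substituting the worst post-baseline value but keeping three flags corrects 0.8 / 8.5 / 0.9 to To High. It leaves 1.5 to 8.5 as H to H. Counting children at the protocol's multiples over all post-baseline values catches every path that reaches 8xULN.

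**The case against.** The strongest reply is that this is a matter of display. The row describes movement of flags and is labelled To Normal as well as No Change. The study is descriptive, so no inference depends on it. With about 120 children per arm, the few large elevations can be counted from Listing 12. The arm maximum, the outside-range counts and the SAE route all give the reader a signal.

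Most of this stands, and it rules out three stronger readings.

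- A reader might infer that children at the stopping limit go unseen, or that the tables can show no liver signal. The documents do not support that, because of the displays set out in Step 3.
- A reader might infer that raised baselines are to be expected. The protocol permits stable chronic liver disease and chronic stable hepatitis B and C, but gives no frequency in children aged 2 to 12 with allergic rhinitis. Nor does the exclusion start at ALT above 2xULN alone; it joins ALT with bilirubin.
- A reader might infer that leaving out unscheduled visits hides peaks on a material scale. The only scheduled post-baseline draw is Visit 5 or Early Withdrawal, and the last dose is on the morning of Visit 5. Weekly repeats would mostly follow a value that is already in the table. Exceptions need an ad hoc test during treatment, or monitoring that began from a raised Visit 1 value.

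The reply does not meet the remaining point. A listing is not an incidence by arm, an arm maximum shows one child and not a count, and the adverse event route for an isolated ALT rise depends on judgement.

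**Conclusion.** The point holds as a reporting gap of limited size. As printed, the shift rule places any rise within high, up to and beyond 8xULN, in the same row as stability and improvement, while a move from normal to 1.1xULN is To High. The table can therefore rank the smaller change as the worse one. Separately, no planned display counts children by arm at the protocol's own ALT and bilirubin multiples.

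The conclusion rests on the rule being programmed as written and on at least one child entering with ALT above ULN. The number of such children cannot be derived from the documents and is probably small. The unscheduled-visit exclusion adds only a narrow further gap. Nothing here weakens the stopping and reporting rules for the individual child. It is a cheap improvement that is worth making before unblinding, and it does not threaten the trial's conclusions.

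**What to change.** 1. In Tables 3.34 to 3.37, print the full 3x3 shift, or at least separate H to H and L to L from the movements to normal, and amend SAP 11.6.3 to match.
2. Add one liver table by arm, for the ITT and Subset ITT populations. Count children whose maximum post-baseline value, scheduled or unscheduled and expressed as a multiple of the local ULN, reaches ALT 3x, 5x and 8xULN, bilirubin 2xULN, and ALT 3xULN with bilirubin 2xULN. State whether the combined count requires both values from the same draw and how the direct-bilirubin fraction is used.
3. Cite these protocol multiples in SAP Appendix 8 in place of "Not applicable", and exempt the new table from the unscheduled-visit and first-valid-value rules.
4. Take the duration-based and symptom-based criteria of Protocol Appendix 2 from the liver event CRF. They cannot be read from a single worst value.
5. Reconcile Protocol 5.5.1.1, under which premature discontinuation of drug means withdrawal from the study, with Appendix 2, under which a child may remain for follow-up assessments after a liver stopping event. The two differ on which draw becomes the endpoint value.

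Items 1 to 4 need SAP wording and one or two extra tables from data already collected; item 5 needs a clarification of the protocol text. The downside is a few more rows, most of them zero.

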Nasal events	A review of nasal events concluded that there was a reasonable possibility that rhinalgia, nasal discomfort (nasal burning, nasal irritation, nasal soreness) and nasal dryness were associated with the use of FFNS. Epistaxis and nasal ulceration are known class effects of intranasal corticosteroids. To complement the adverse event and nasal examination data and to characterise further effect on the nasal mucosa, GSK initiated a nasal biopsy study FFR104503. This study did not identify any new safety concerns for FFNS.	Focused nasal examinations will be conducted with grading system. Nasal examination will be one of the safety endpoints. Review AE and SAE reports.

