7.5.3. Nasal Exams

A detailed nasal examination of the mucosa, septum, secretions, nasal patency, size of any polyps and ulcers will be performed by the investigator at all visits (Visits 1 – 5 or Early Withdrawal) and the findings recorded on the nasal examination CRF page. Any unfavorable changes that are not reflective of the symptoms of AR from the Visit 1 assessment will be recorded as an adverse event, documenting the start and stop dates of the adverse event. A diagnosis of nasal candidacies should be reported as an adverse event.

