9.4.3. Other Analyses

Safety analysis

Safety data will be summarized and/or listed by treatment group for the ITT population.

Extent of Exposure

The extent of exposure to study drug will be summarized by treatment group.

Adverse Events (AEs)

AEs will be coded using the standard GSK dictionary, MedDRA, and grouped by body system. AEs occurring pre-treatment, during active treatment and post-treatment will be summarized separately. The number and percentage of subjects experiencing at least one AE of any type, AEs within each body system and AEs within each preferred term will be presented for each treatment group. Separate summaries will be provided for all AEs, drug related AEs, SAEs, and for AEs leading to withdrawal.

Clinical Laboratory Evaluations

Clinical laboratory evaluations, including hematological and clinical chemistry, will be summarized by treatment group for each visit. Further details will be provided in the RAP.

Nasal Examinations

Nasal examinations will be performed at each visit, and will include assessments of nostril patent, septum, mucosa, secretions, ulcers, and polyposis. Nasal examination results will be summarized by visit for each of the 6 examination parameters listed above. At all visits, frequencies of classifications (yes/no, absent/present) will be calculated. Shift from baseline (Visit 2) will be summarized for each individual nasal examination parameter. Abnormal nasal examination results will be listed.

Vital Signs Assessments

Vital signs will be summarized for each clinic visit. Further details will be provided in the RAP.

Deaths and SAEs

All SAEs will be tabulated and listed by treatment group. Deaths and SAEs will be documented in case narrative format.

10. STUDY GOVERNANCE CONSIDERATIONS**10.1. Posting of Information on Publicly Available Clinical Trial Registers**

Study information from this protocol will be posted on publicly available clinical trial registers before enrollment of subjects begins.

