3.37.	Subset Intent-to-Treat	ffr30008-01-body-csr Table 8.35	Summary of Chemistry Shifts from Baseline to Endpoint		SAC
3.38.	Intent-to-Treat	ffr30008-01-body-csr Table 8.35	Summary of Urinalysis Shifts from Baseline to Endpoint		SAC
3.39.	Subset Intent-to-Treat	ffr30008-01-body-csr Table 8.35	Summary of Urinalysis Shifts from Baseline to Endpoint		SAC
3.40.	Intent-to-Treat	ffr30008-01-body-csr Table 8.42	Summary of Nasal Examinations		SAC

Safety : Tables					
No.	Population	IDSL / TST ID / Example Shell	Title	Programming Notes	Deliverable [Priority]
3.41.	Subset Intent-to-Treat	ffr30008-01-body-csr Table 8.42	Summary of Nasal Examinations		SAC
3.42.	Intent-to-Treat	ffr30008-01-body-csr Table 8.43	Summary of Nasal Examination Shifts from Baseline to Endpoint		SAC
3.43.	Subset Intent-to-Treat	ffr30008-01-body-csr Table 8.49	Summary of Nasal Examination Shifts from Baseline to Endpoint		SAC
3.44.	Intent-to-Treat	ffr30008-01-body-csr Table 8.70	Summary of Vital Signs		SAC
3.45.	Subset Intent-to-Treat	ffr30008-01-body-csr Table 8.70	Summary of Vital Signs		SAC
3.46.	Intent-to-Treat	ffr30008-01-body-csr Table 8.71	Summary of Change from Baseline in Vital Signs at Endpoint		SAC
3.47.	Subset Intent-to-Treat	ffr30008-01-body-csr Table 8.71	Summary of Change from Baseline in Vital Signs at Endpoint		SAC
3.48.	Intent-to-Treat	ffr30008-01-body-csr Table 8.70	Summary of ECG		SAC
3.49.	Subset Intent-to-Treat	ffr30008-01-body-csr Table 8.70	Summary of ECG		SAC
3.50.	Intent-to-Treat	ffr30008-01-body-csr Table 8.71	Summary of Change from Baseline in ECG at Endpoint		SAC

Safety : Tables					
No.	Population	IDSL / TST ID / Example Shell	Title	Programming Notes	Deliverable [Priority]
3.51.	Subset Intent-to-Treat	ffr30008-01-body-csr Table 8.71	Summary of Change from Baseline in ECG at Endpoint		SAC
3.52.	Intent-to-Treat	ffr30008-01-body-csr Table 8.72	Summary of ECG Findings		SAC
3.53.	Subset Intent-to-Treat	ffr30008-01-body-csr Table 8.72	Summary of ECG Findings		SAC

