11.14.10. ICH Listings

ICH : Listings					
No.	Population	IDSL / TST ID / Example Shell	Title	Programming Notes	Deliverable [Priority]
Study Population					
1.	Per Protocol	ffr30008-01-body-csr Table 6.2	Listing of Reasons for exclusion from Per-Protocol		SAC
2.	Intent-to-Treat	ffr30008-01-body-csr Table 6.11	Listing of Subject Withdrawals: End of Study Record		SAC
3.	Intent-to-Treat	ffr30008-01-body-csr Table 6.24	Listing of Inclusion/Exclusion/Randomization Criteria Deviations		SAC
4.	Intent-to-Treat	ffr30008-01-body-csr Table 6.31	Listing of Important Protocol Deviations		SAC
Safety					
5.	Intent-to-Treat	ffr30008-01-body-csr Table 8.4	Listing of Exposure		SAC
6.	Intent-to-Treat	ffr30008-01-body-csr Table 8.14	Listing of All Adverse Events		SAC
7.	Intent-to-Treat	ffr30008-01-body-csr Table 8.17	Listing of Drug-Related Adverse Events During the Study Period		SAC
8.	Intent-to-Treat	ffr30008-01-body-csr Table 8.20	Listing of Serious Adverse Events		SAC
9.	Intent-to-Treat	ffr30008-01-body-csr Table 8.22	Listing of Adverse Events Leading to Discontinuation of Study Treatment		SAC
10.	Intent-to-Treat	ffr30008-01-body-csr Table 8.14	Listing of All Adverse Events for On-treatment Adverse Events of Special Interest		SAC
11.	Intent-to-Treat	ffr30008-01-body-csr Table 8.36	Listing of Laboratory Data for Subjects with at Least One Abnormal Value Post-Randomization in Haematology		SAC
12.	Intent-to-Treat	ffr30008-01-body-csr Table 8.37	Listing of Laboratory Data for Subjects with at Least One Abnormal Value Post-Randomization in Chemistry		SAC

ICH : Listings					
No.	Population	IDSL / TST ID / Example Shell	Title	Programming Notes	Deliverable [Priority]
13.	Intent-to-Treat	ffr30008-01-body-csr Table 8.37	Listing of Laboratory Data for Subjects with at Least One Abnormal Value Post-Randomization in Urinalysis		SAC
14.	Intent-to-Treat	ffr30008-01-body-csr Table 8.46	Listing of Subjects with at Least One Abnormal Nasal Examination Result Post-Baseline		SAC
15.	Intent-to-Treat	ffr30008-01-body-csr Table 8.73	Listing of Subjects with at Least One Abnormal Clinically Significant and/or Clinically Significant Change in ECG from Baseline Classification		SAC

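### The nasal-examination shift is tabulated at Visit 5 or early withdrawal only, so a finding new at Visit 3 or 4 and healed by Visit 5 counts as no shift; a worst-post-baseline shift would be a cheap addition

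*SAP*

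**What the plan says.** Protocol 4.5.1 lists nasal events as a risk, with epistaxis and nasal ulceration as class effects. Its mitigation is that "Focused nasal examinations will be conducted with grading system", and nasal examination is made a safety endpoint. Under the Time and Events Table (Protocol 7.1) the nose is examined at every clinic visit and at early withdrawal. The three scheduled on-treatment examinations are Visit 3 (Day 8), Visit 4 (Day 15) and Visit 5 (Day 29), each ±2 days.

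For analysis, Protocol 9.4.3 covers six parameters: patency, septum, mucosa, secretions, ulcers and polyposis. It plans by-visit results ("At all visits, frequencies of classifications (yes/no, absent/present) will be calculated") and a shift: "Shift from baseline (Visit 2) will be summarized for each individual nasal examination parameter". It does not say to which post-baseline visit or visits the shift runs.

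SAP 11.6.3 keeps the by-visit part: "Summary statistics for mucosa, septum, secretions, nasal patency, size of any polyps and ulcers will be provided at Visit 1-5 or Early Withdrawal". For the comparison with baseline it says: "A summary of change from baseline in nasal examinations at endpoint (Vsit5/Early Withdrawal) will be made". The matching displays in SAP 11.14.8, Tables 3.42 (ITT) and 3.43 (ages 2 to 6), are titled "Summary of Nasal Examination Shifts from Baseline to Endpoint". No shift table for Visit 3, Visit 4 or the worst post-baseline examination is listed.

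Two other routes carry nasal findings. SAP 11.14.10 plans Listing 14, "Listing of Subjects with at Least One Abnormal Nasal Examination Result Post-Baseline". Protocol 7.5.3 provides that "Any unfavorable changes that are not reflective of the symptoms of AR from the Visit 1 assessment will be recorded as an adverse event".

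**The concern.** An endpoint-only comparison loses little for laboratory tests, vital signs and ECG, because each has one scheduled post-baseline assessment (Visit 5 or early withdrawal). SAP 11.6.3 uses the same rule and almost the same sentence for nasal examinations as for vital signs. Nasal examinations, however, have three scheduled on-treatment looks, and the rule leaves two of them out of the tabulated comparison with the child's own baseline.

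Ulceration from a nasal spray may be transient. A child who is clear at Visit 2, ulcerated at Visit 3 and healed by Visit 5 sits in the no-shift cell beside a child who never had a lesion. At stake is how well one safety display describes a named local risk. No efficacy result depends on it.

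**Working it through.** The plan states no figure on this point, so there is none to reproduce. The check has two parts.

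**1. What each planned display can show for a finding new at Visit 3 or 4 and gone by Visit 5**

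| Display | By arm? | Compared with child's baseline? | Catches the finding? |
|---|---|---|---|
| Tables 3.42/3.43, shift to endpoint | Yes | Yes | No |
| Tables 3.40/3.41, by-visit summary | Yes | No | Yes, as prevalence at that visit |
| Listing 14, any abnormal post-baseline result | No comparative summary | No | Yes, as a line in a listing |
| Tables 3.05/3.06, treatment-period AEs | Yes | Yes, against Visit 1, by investigator judgement | If recorded as an AE |

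By-visit prevalence does not count children. Two ulcers at Visit 3 and two at Visit 4 may be two, three or four children, and a finding already present at baseline is not separated from a new one. Listing 14 admits any abnormal result. Protocol 5.1 makes nasal signs (pale mucosa, oedema, secretion) part of the diagnosis, so children may be listed for the disease itself. AE recording depends on judging a change not to be part of AR. No row gives, by arm, the number of children with a new or worse examination finding at any on-treatment visit.

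**2. How much the endpoint table can miss**

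The examination days (8, 15 and 29) are the nominal days in Protocol 7.1. Two inputs are assumptions, since the documents give neither: onset is uniform over the 28 days from Day 1 to Day 29, and each lesion lasts *d* days. A lesion is present on an examination day if its onset fell within the *d* days before it.

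- **d = 7.** Present on Day 29: 7/28 = 25%. The onset intervals for Days 8, 15 and 29 do not overlap, so present at any examination: 3 × 7/28 = 75%. Ratio: 25/75 = 1/3.
- **d = 14.** Present on Day 29: 14/28 = 50%. Onsets from Day 1 to Day 15 are seen by Day 15 and the rest on Day 29, so present at any examination: 28/28 = 100%. Ratio: 50/100 = 1/2.
- **Lesion persists to Day 29.** The endpoint examination sees it. Ratio: 1.

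In numbers of children, take the planned 120 per arm, an assumed share *p* with a new finding at Visit 3 or 4, and an assumed share *h* of those healed by Visit 5. The examinations find 120 × p, and the endpoint shift shows 120 × p × (1 − h).

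| p | Found at Visit 3/4 | Endpoint shift, h = 0.25 | h = 0.5 | h = 1 |
|---|---|---|---|---|
| 2% | 2.4 | 1.8 | 1.2 | 0 |
| 5% | 6.0 | 4.5 | 3.0 | 0 |
| 10% | 12.0 | 9.0 | 6.0 | 0 |

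These are illustrations of one table's yield. They are not estimates of what the study report as a whole would lose.

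**The case against.** The strongest reply is that the finding reaches the report by other routes. The by-visit tables are presented by treatment group, and in randomised arms a difference in ulcer prevalence at Day 8 or Day 15 is a valid comparison. Listing 14 covers every post-baseline visit. Protocol 7.5.1.3 refers to Section 4.5.1 for AEs of special interest, and SAP Listing 10 lists those that occur on treatment. For ulcers the AE judgement is not hard, since the nasal symptoms in Protocol 7.4.1 are congestion, itching, rhinorrhea and sneezing; it matters mainly for mucosa and secretions. The study is descriptive and plans no safety modelling. All of this stands, and it makes the gap small. It does not supply a per-child, by-arm count of new or worse examination findings.

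Four stronger readings are tempting, and the documents do not support them.

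- **That the SAP departs from the protocol while SAP 2.1 declares no changes.** Protocol 9.4.3 names no post-baseline visit for the shift. The SAP fills an open point, though narrowly.
- **That the shift table is the only structured measure of nasal risk.** Epistaxis and irritation are not among the six parameters, so no shift table would measure them. AEs are coded and tabulated by arm.
- **That a difference between a dose and placebo is hidden.** It can be understated in the shift table, but the by-visit and AE tables remain.
- **That the shift is limited to yes/no.** That wording in Protocol 9.4.3 describes the by-visit frequencies. The shift sentence gives no scale, SAP 11.6.3 mentions the size of polyps and ulcers, and the table shells sit in an earlier study report that is not available here.

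**Conclusion.** The point holds as a low-severity improvement. The one planned nasal shift runs to Visit 5 or early withdrawal, so two of the three scheduled on-treatment examinations do not enter it. A transient finding at Visit 3 or 4 is counted as no shift, and no other examination table counts affected children by arm.

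The understatement within Tables 3.42 and 3.43 ranges from none, for lesions that persist to Day 29, to about two thirds of detected lesions lasting 7 days. That range rests on uniform onset, nominal visit days and assumed durations. The conclusion about what the displays can count rests on the text alone.

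**What to change.** In SAP 11.6.3 and Tables 3.42 and 3.43, keep the endpoint shift. Beside it, add the shift from the last pre-dose examination to the worst post-baseline examination (Visits 3, 4, 5 and early withdrawal), by arm, for each of the six parameters. Use the recorded grade or size where one was collected. State for each parameter what counts as worst, and settle this before unblinding.

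The cost is a few lines of SAP text and one extra column per table, with no new examination or data item. The downside is that worst-of-three counts will be higher than endpoint counts in every arm, placebo included. The column should be read as a comparison between arms, and a footnote should say so.
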